3.1 Adverse Event Monitoring

All clinically significant adverse events (AEs), whether or not considered to be expected or unexpected and whether or not considered to be associated with the use of study drug, will be entered into OnCore, UCSF's Clinical Trial Management System.

Adverse events are graded according to the Common Terminology Criteria for Adverse Events (CTCAE) as developed and revised by the Common Therapy Evaluation Program (CTEP) of the National Cancer Institute. Adverse events are further given an assignment of attribution or relationship to investigational agent or study procedure. Attribution categories are:

- Definite clearly related to the investigational agent(s) or study procedure.
- **Probable** likely related to the investigational agent(s) or study procedure.
- Possible may be related to the investigational agent(s) or study procedure.
- **Unrelated** clearly not related to the investigational agent(s) or study procedure.

All adverse events entered into OnCore will be reviewed on a weekly basis at the UCSF Coordinating Center's Site Committee meetings. The UCSF Site Committee will review and discuss the selected toxicity, grade, and the attribution assignment for the adverse events that occurred at both the UCSF Coordinating Center and the participating sites.

3.2 Serious Adverse Event Reporting

By definition, an adverse event is defined as a serious adverse event (SAE) according to the following criteria:

- · Death,
- Life-threatening adverse experience*,
- Inpatient hospitalization or prolongation of existing hospitalization,
- Persistent or significant disability/incapacity,

Congenital anomaly/birth defect, or cancer, or

- Any other experience that suggests a significant hazard, contraindication, side
 effect or precaution that may require medical or surgical intervention to prevent one
 of the outcomes listed above,
- Event that changes the risk/benefit ratio of the study.
- * A life-threatening adverse experience is any AE that places the patient or subject, in the view of the investigator, at immediate risk of death from the reaction as it occurred, i.e., it does not include a reaction that, had it occurred in a more severe form, might have caused death.

Serious adverse event reporting will be in accordance with all IRB regulations. For trials conducted under an investigational new drug (IND) application, the SAE will be reported in accordance with Code of Federal Regulation Title 21 Part 312.32 and will be reported on a Med Watch form.

UCSF IRB website for guidance in reporting serious adverse events:

https://irb.ucsf.edu/adverse-event

Med Watch forms and information:

www.fda.gov/medwatch/getforms.htm

All serious adverse events are entered into OnCore, as well as submitted to the IRB (per IRB guidelines). All SAEs, whether expected or unexpected, must be reported to the UCSF Coordinating Center within 10 business days of becoming aware of the event or during the next scheduled conference all, whichever is sooner. The SAEs are reviewed and monitored by the Data and Safety Monitoring Committee on an ongoing basis and discussed at DSMC meetings, which take place every six weeks. The date the SAE was sent to all required reporting agencies will be documented in OnCore.

If a death occurs during the treatment phase of the study or within 30 days after the last administration of the study drug(s) and is determined to be possibly, probably, or definitely related either to the investigational drug or any research related procedure, the Study Chair at the UCSF Coordinating Center or the assigned designee must be notified within 1 business day from the participating site(s) and the Study Chair must then notify the DSMC Chair (or Vice Chair) and the DSMC Director within one business day of this notification.

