2.1 Primary objectives

- 1. Part 1: Escalation Cohort: Maximum tolerated dose (MTD) of sorafenib in combination with standard dose nivolumab with Child Pugh A-B7 liver function
- 2. Part 2: Child Pugh B Expansion Cohort: Safety in patients with Child Pugh B liver function

2.2 Secondary objectives for Parts 1 and 2

- 1. Safety and tolerability of combination overall
- 2. Rate of irAE for combination overall and in patients with Child Pugh B liver function
- 3. Objective response rate (ORR) by RECIST 1.15 for overall study
- 4. ORR by RECIST 1.1 in patients with Child Pugh B liver function
- 5. Duration of response (DOR), progression free survival (PFS), and overall survival (OS) for Escalation Cohort and Child Pugh B Expansion Cohort and overall

2.3 Exploratory objectives for Parts 1 and 2

- Relationship between PBMC immune cell subset frequencies, baseline liver function, and clinical outcomes
- 2. Relationship between PBMC T cell receptor (TCR) clonotype frequency and diversity, baseline liver function, and clinical outcomes
- 3. Tumor tissue immune cell subsets and TCR clonotype frequency and diversity in pre-treatment archival tumor tissue samples

4.

- 5. Tumor and immune cell PD-L1 status in pre-treatment archival tumor tissue samples and relationship to clinical outcomes
- 6. Changes in HBV and/or HCV viral load on treatment
- 7. AFP changes on treatment and relationship to clinical outcomes
- Relationship between clinical outcomes and clinicopathologic features including race/ethnicity, etiology of liver disease including HBV/HCV status, baseline liver function, presence of cirrhosis, macrovessel invasion, extrahepatic spread, site(s) of metastatic disease, prior treatment history including prior radiation and arterial therapies

3. Investigators and other study participants

Principal Investigator: [name]

Associate Professor of Clinical Medicine

University of California, San Francisco (UCSF)

A second study site, University of California, Davis (UCD) was activated after completion of Part 1: Dose Escalation Cohort.

4. Study design

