7.4.2 Reporting of SAE to Bayer

All SAEs occurring from date of informed consent until 100 days after last dose of protocol therapy regardless of attribution should be reported to Bayer within 24 business hours/1 business day using a MedWatch Form 3500A (which can be accessed at http://www.accessdata.fda.gov/scripts/medwatch/ and in Appendix 14.9), using one of the mechanisms below. Any serious adverse events (SAE) occurring later than 100

days after the last dose of protocol therapy also should be recorded and reported if assessed as at least possibly related to study drug or a protocol-specified procedure.

Bayer SAE Electronic Mailbox:

Bayer SAE Facsimile:

Bayer USPS Address:

Global Pharmacovigilance - USA

Bayer Corporation

Reports for all Bayer products can also be phoned in via the Clinical Communications Dept.:

Bayer SAE Phone: (Medical Communications)

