7.4.5 IND safety reporting

UCSF will report to the FDA all IND reportable events occurring in patients enrolled on this study (at UCSF or sub-site) using FDA Medwatch Form 3500A (which can be accessed at http://www.accessdata.fda.gov/scripts/medwatch/ and in Appendix 14.9). Reportable events must meet the definition in Federal Regulations (21 CFR §312.32):

- 1. Suspected adverse reaction (defined as a reasonable possibility that the investigational agent caused the adverse event)
- 2. Unexpected (not listed in the investigator brochure or package insert(s), or is not listed at the specificity or severity that has been observed)
- 3. Serious (as defined in Section 7.4.1.2)

If the adverse event does not meet all three of the definitions, it should not be submitted as an expedited IND safety report. The timeline for submitting an IND safety report to FDA is no later than 15 calendar days after the Investigator determines that the suspected adverse reaction qualifies for reporting (21 CFR 312.32(c)(1)). Any unexpected fatal or life-threatening suspected adverse reaction will be reported to FDA no later than 7 calendar days after the Investigator's initial receipt of the information (21 CFR 312.32(c)(2)).

Any relevant additional information that pertains to a previously submitted IND safety report will be submitted to FDA as a Follow-up IND Safety Report without delay, as soon as the information is available (21 CFR 312.32(d)(2)).

A copy of all 15 Day Reports and Annual Progress Reports will be submitted as required by FDA.

The Study Chair or designee will cross reference this submission according to local regulations to the Bayer and/or BMS Investigational Compound Number (IND) at the time of submission, based upon investigator attribution of causality. Additionally, Study Chair or designee will submit a copy of these reports to Bayer and BMS at the time of submission to FDA.

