9.8 Multicenter communication

The UCSF Coordinating Center provides administration, data management, and organizational support for the participating sites in the conduct of a multicenter clinical trial. The UCSF Coordinating Center will also coordinate, at weekly conference calls with the participating sites for Phase I dose escalation studies prior to each cohort escalation and at the completion of each cohort or more frequently as needed to discuss risk assessment. The following issues will be discussed as appropriate:

- Enrollment information
- Cohort updates (i.e. DLTs) and enrollment status
- Adverse events (i.e. new adverse events and updates on unresolved adverse events and new safety information)
- Protocol violations
- Other issues affecting the conduct of the study

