DSMC Monitor/Auditors will send a follow-up report to the study team within 20 business days after the monitoring visit is complete for the PI and the study team to resolve all action items from this report within 20 business days. An abbreviated regulatory review (i.e., reviewing protocol and consent versions, SAEs, PVs, DOA logs, 1572 forms, etc.) will occur at each participant monitoring review; however, a full regulatory review will occur on a biennially basis by the DSMC for regulatory compliance.

Monitoring of enrolled participants in the dose expansion portion of the trial will be complete after 20% of enrolled participants have been monitored through two cycles of treatment. However, regulatory reviews of the trial, safety reviews (i.e., Serious Adverse Event (SAE) reviews and Protocol Violation (PV) reviews), as well as audit/inspection preparation (as applicable) will continue until the trial is closed by the IRB.

Multicenter communication

The UCSF Coordinating Center includes the UCSF PI (Study Chair) and the UCSF study team. The UCSF Coordinating Center and provides administration, data management, and organizational support for the participating sites in the conduct of a multicenter clinical trial. The UCSF Coordinating Center will also coordinate monthly conference calls with the participating sites. The following issues will be discussed as appropriate:

- Enrollment information.
- Cohort updates (i.e., DLTs).
- Adverse events (i.e., new adverse events and updates on unresolved adverse events and new safety information).
- Protocol violations.
- Other issues affecting the conduct of the study.

Dose Level Considerations

The PI/Study Chair, participating investigators, and research coordinators from each site will review enrollment for each dose level cohort during the regularly scheduled conference calls. The dose level for ongoing enrollment will be confirmed for each participant scheduled to be enrolled at a site. Dose level assignments for any participant scheduled to begin treatment must be confirmed by the UCSF Coordinating Center via email.

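### The sub-site may take up to 10 business days to tell UCSF of an SAE, although UCSF files FDA reports for both sites (7 calendar days for the most serious) and Bayer must have the same form in 1 business day

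*Combined protocol and SAP*

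**What the plan says.** Five places in the combined protocol and SAP bear on how fast a sub-site SAE travels.

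- **Sub-site to UCSF.** Appendix 11, section 3.2 says that all SAEs, expected or not, "must be reported to the UCSF Coordinating Center within 10 business days of becoming aware of the event", or at the next scheduled conference call if that is earlier. The paragraph that follows shortens this to 1 business day for deaths at least possibly related to drug or procedure, if they occur on treatment or within 30 days of the last dose.
- **UCSF to FDA.** Section 7.4.5 makes UCSF the reporter for events at both sites. "Any unexpected fatal or life-threatening suspected adverse reaction will be reported to FDA no later than 7 calendar days", counted from the Investigator first receiving the information. Other IND safety reports have 15 calendar days, counted from the Investigator's determination that the reaction qualifies.
- **Site to Bayer.** Section 7.4.2 says that SAEs "regardless of attribution should be reported to Bayer within 24 business hours/1 business day", on MedWatch Form 3500A.
- **Recipients.** Appendix 9 lists Bayer, BMS and UCSF as recipients of sub-site reports and repeats that UCSF makes the IND submissions. It sets no time limit for the copy to UCSF.
- **Calls.** In Appendix 11 the coordinating centre "will also coordinate monthly conference calls with the participating sites". Section 9.8 instead speaks of contact "at weekly conference calls with the participating sites for Phase I dose escalation studies". Section 3 says that the second site "was activated after completion of Part 1: Dose Escalation Cohort".

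**The concern.** The drug company may hold a sub-site SAE well before the party that must file it with the FDA is due to be told. For an unexpected, life-threatening, non-fatal suspected reaction, the time allowed for the first step (sub-site to UCSF) is longer than the whole time allowed for the FDA report.

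The primary endpoint of Part 2 is the rate of grade ≥3 treatment-related AEs in patients with Child Pugh B liver function (Section 8.2.1.2). Appendix 11 makes the Study Chair responsible for safety at all sites under continuous review, and for alerting the DSMC if grade 3 or 4 rates rise. Neither duty can be carried out for events that have not arrived, and enrolment may continue in the meantime.

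**Working it through.** The plan gives no figure to reproduce, so the check converts the limits to a common scale and compares them.

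**Step 1: 10 business days in calendar days (no holidays).**

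| Day sub-site becomes aware | 1 business day | 10 business days | Past a 7-day limit |
|---|---|---|---|
| Mon to Thu | 1 day | 14 days | 14 − 7 = 7 |
| Fri | 3 days | 14 days | 14 − 7 = 7 |
| Sat | 2 days | 13 days | 13 − 7 = 6 |
| Sun | 1 day | 12 days | 12 − 7 = 5 |

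Bayer's report is therefore due in 1 to 3 calendar days and UCSF's in 12 to 14. The last column assumes that the 7-day clock starts when the sub-site investigator becomes aware.

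**Step 2: the 15-day limit.** If the sub-site investigator also made the determination on the day of awareness, 15 − 14 = 1 to 15 − 12 = 3 days would remain when UCSF hears. Section 7.4.5 counts from determination, so this is an illustration and not a general result.

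**Step 3: how much the call alternative shortens the delay.** The permitted delay is the smaller of the time to the next call and the 10-business-day limit. Let T be the number of days between calls, and assume that awareness is spread evenly between calls.

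- Share permitted to arrive after day 7 = (T − 7)/T. For T = 28: 21/28 = 75%. For T = 31: 24/31 = 77%.
- Share permitted the full 14 days = (T − 14)/T, ignoring the slightly shorter weekend limit. For T = 28: 14/28 = 50%. For T = 31: 17/31 = 55%.
- With weekly calls (T = 7) the share beyond day 7 is 0.

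The call frequency therefore decides whether the alternative protects anything. The weekly frequency in Section 9.8 is worded for dose escalation, which ended before the sub-site opened. That leaves the monthly frequency in Appendix 11 as the one that plainly applies.

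**Step 4: do other rules close the gap?**

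- The 1-business-day death rule does not reach non-fatal life-threatening reactions, or related deaths more than 30 days after the last dose. SAE collection runs to 100 days.
- The 1-business-day DLT notice in Appendix 11 concerns a Part 1 endpoint (Section 8.1.1). The sub-site took no part in Part 1.
- The weekly Site Committee review (Appendix 11, section 3.1) covers events already entered in OnCore. Section 9.6 asks for entry as soon as possible after the visit and gives no deadline.

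**Step 5: enrolment during the gap.** Over about half a month, the stated 1 to 2 patients per month (Section 4.5.1) gives 0.5 × 1 = 0.5 to 0.5 × 2 = 1 patient. The abstract's maximum of 24 patients over 48 months averages 0.5 per month, which gives 0.5 × 0.5 = 0.25 patient. Both are trial-wide figures.

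**The case against.** A reader might infer that the plan makes UCSF miss the FDA deadline. The documents do not establish this. The 7-day clock starts when the Investigator first receives the information, and Section 7.4.5 does not say which investigator. UCSF is the reporter there, and Section 9.5 refers to a sponsor-investigator. If that is who is meant, the clock has not started before UCSF is told, and nothing is late under 7.4.5.

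A reader might also take the monthly call as a way to extend the 10 business days. It cannot: the earlier of the two applies, so a call can only shorten the delay.

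The best practical defence is that Appendix 9 already sends the sub-site's report to UCSF as well as Bayer, and that the Bayer copy is due in 1 business day. The natural practice is one form sent to all recipients at once, with 10 business days as an outer limit. Appendix 11, section 3.2 also requires reporting in line with 21 CFR 312.32, and OnCore gives UCSF a parallel view. Most fatal events under the 7-day rule have their own 1-business-day limit.

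These points make a long delay less likely in practice, and they limit the gap mainly to non-fatal life-threatening reactions. They do not remove it. The only explicit time limit for UCSF to be told of such a reaction is the one in Appendix 11, section 3.2, and a sub-site that uses all of it complies with the plan.

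**Conclusion.** The limits are inconsistent as written and should be changed. A non-fatal life-threatening reaction, or a related death more than 30 days after the last dose, may properly reach UCSF 12 to 14 calendar days after the sub-site learns of it (longer with holidays), unless a call comes first. Bayer must have it in 1 to 3.

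The consequence for the FDA deadline depends on a point that the text leaves open:

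- If the sub-site investigator's receipt starts the clock, a report that complies with Appendix 11 can reach UCSF 5 to 7 days after the 7-day limit has passed.
- If the UCSF investigator's receipt starts it, no deadline is formally missed, but notice to the FDA and awareness by the Study Chair and DSMC are still delayed.

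The 75–77% share rests on monthly calls and evenly spread events. It describes what is permitted and does not predict what sites will do. The number of patients who might start treatment in the gap is at most about one. The case for change rests on timely oversight of a cohort whose primary endpoint is safety. It does not need a stronger description of the population: Appendix 3 reserves the term decompensated for Child Pugh C, and Part 2 enrols class B.

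**What to change.** - **Appendix 11, section 3.2:** require the sub-site to send every SAE to UCSF within 1 business day of awareness, on the MedWatch form and timeline already used for Bayer. Remove the conference-call alternative, which then serves no purpose.
- **Section 7.4.5:** state whose receipt of the information starts the 7-day clock and whose determination starts the 15-day clock.
- **Section 9.8 and Appendix 11:** give one call frequency for Part 2.
- **Appendix 9:** add the same 1-business-day limit for the copy to UCSF.

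The cost is a few sentences and almost no added site work, since the sub-site already completes the same form within 1 business day. The change needs the usual amendment approvals (Sections 9.4 and 12.1). Section 9.7 describes the monitoring plan as NCI-approved. If its wording cannot easily be altered, the 1-business-day limit can stand in Section 7.4 of the protocol, with a statement that it takes precedence over Appendix 11.

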3.3 Review of Adverse Event Rates

If an increase in the frequency of Grade 3 or 4 adverse events (above the rate reported in the Investigator Brochure or package insert) is noted in the study, the Study Chair at the UCSF Coordinating Center is responsible for notifying the DSMC at the time the increased rate is identified via a report. The report will indicate if the incidence of adverse events observed in the study is above the range stated in the Investigator's Brochure or package insert.

If at any time the Study Chair voluntarily holds enrollment or stops the study due to safety issues, the DSMC Chair (or Vice Chair) and the DSMC Director must be notified within one business day via e-mail and the IRB must be notified their reporting requirements.

